#### Secondary outcomes

- ! Early definitive treatment rate in 2019 vs. 2020: defined as treatment in accordance with the current guidelines (cholecystectomy or ERCP with endoscopic sphincterotomy during the same hospital admission or within 2 weeks of discharge)
- ! 30-day hospital readmission rate in 2019 vs. 2020: defined as hospital readmission within 30days from discharge for recurrent biliary AP while awaiting interval cholecystectomy, or due to post-cholecystectomy complications
- ! Predictive factors of morbidity and mortality in patients with biliary AP

The compliance of surgeons to the most up-to-date international guidelines on biliary AP will be assessed through the analysis of the following attitudes:

! Use of scoring systems for the diagnosis and severity grading of biliary AP

- ! Use of lipase dosage (for the diagnosis) and CRP (for the severity grading) during the diagnostic workup
- ! Use of Ultrasound scan, CT scan, MRCP, and endoscopic Ultrasound scan (EUS) in the correct way and timing
- ! Use of early ERCP and sphincterotomy in case of cholangitis and/or choledocholithiasis
- ! Use of percutaneous and/or endoscopic drainage in case of infected pseudocyst or necrosis
- ! Timing of surgical necrosectomy
- ! Timing of re-laparotomy in case of open abdomen strategies
- ! Use of prophylactic antibiotics/antifungals
- ! Use of somatostatin analogs
- ! Use of early enteral feeding
- ! Use of early definitive treatment strategies, including cholecystectomy and/or ERCP and sphincterotomy

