21. Surgical strategy	
 
! In infected pancreatic necrosis, percutaneous drainage as the first line of treatment (step-up approach) delays the surgical treatment to a more favorable time or even results in complete resolution of infection in 25–60% of patients and it is recommended as the first line of treatment (1A).
 
! Minimally invasive surgical strategies, such as transgastric endoscopic necrosectomy or videoassisted retroperitoneal debridement (VARD), result in less postoperative new-onset organ failure but require more interventions (1B).
 

	
 
! Considering mortality, there is insufficient evidence to support open surgical, mini-invasive, or endoscopic approach (1B).
 
! In selected cases with walled-off necrosis and in patients with disconnected pancreatic duct, a single stage surgical transgastric necrosectomy is an option (2C).
 

	! A multidisciplinary group of experts should individualize surgical
	treatment taking local expertise into account (2C)
22. Timing of cholecystectomy	
 
Laparoscopic cholecystectomy during index admission is recommended in mild acute gallstone pancreatitis (1A).
 
When ERCP and sphincterotomy are performed during the index admission, the risk for recurrent pancreatitis is diminished, but same admission cholecystectomy is still advised since there is an increased risk for other biliary complications (1B).
 
In acute gallstone pancreatitis with peripancreatic fluid collections, cholecystectomy should be deferred until fluid collections resolve or stabilize and acute inflammation ceases (2C).
 

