23. Open abdomen	
 
! In patients with severe acute pancreatitis unresponsive to conservative management of IAH/ ACS, surgical decompression and use of open abdomen are effective in treating the abdominal compartment syndrome (2C).
 
! We suggest that clinicians should be cautious not to over-resuscitate patients with early SAP and measure intra-abdominal pressure regularly (1C).
 
! We suggest that the open abdomen (OA) be avoided if other strategies can be used to mitigate or treat severe intra-abdominal hypertension in SAP (1C).
 
! We recommend not to utilize the OA after necrosectomy for SAP (unless severe IAH mandates OA as a mandatory procedure) (1C).
 
! We recommend not to debride or undertake early necrosectomy if forced to undertake an early OA due abdominal compartment syndrome or visceral ischemia (1A).
 

24. Open abdomen management and temporary abdominal closure	
 
We recommend the use of negative pressure peritoneal therapy for OA management (1B).
 
We suggest fascial traction be added to NPWT methods (2B).
 
We suggest that further controlled studies be conducted on intra- peritoneal osmotic therapies in SAP (no recommendation)
 

25. Timing of dressing changes	! Open abdomen re-exploration should be conducted no later than 24– 48 h after the index and any subsequent operation, with the duration from the previous operation shortening with increasing degrees of patient non-improvement and hemodynamic instability (1C).
26. Timing for abdominal closure	! Early fascial and/or abdominal definitive closure should be the strategy for management of the open abdomen once any requirements for on-going resuscitation have ceased, the source control has been definitively reached, no concern regarding intestinal viability persist, no further surgical re-exploration is needed, and there are no concerns for abdominal compartment syndrome (1B).

From: Leppäniemi A, Tolonen M, Tarasconi A, Segovia-Lohse H, Gamberini E, Kirkpatrick AW, Ball CG, Parry N, Sartelli M, Wolbrink D, van Goor H, Baiocchi G, Ansaloni L, Biffl W, Coccolini F, Di Saverio S, Kluger Y, Moore E, Catena F. 2019 WSES guidelines for the management of severe acute pancreatitis. World J Emerg Surg. 2019 Jun 13;14:27. doi: 10.1186/s13017-019-0247-0. PMID: 31210778; PMCID: PMC6567462.

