	! The nasogastric route for feeding can be used as it appears to be effective in 80% of cases (recommendation grade B).
4. Treatment of gallstones	! Urgent therapeutic endoscopic retrograde cholangiopancreatography (ERCP) should be performed in patients with acute pancreatitis of suspected or proven gallstone etiology who satisfy the criteria for predicted or actual severe pancreatitis, or when there is cholangitis, jaundice, or a dilated common bile duct. The procedure is best carried out within the first 72 hours after the onset of pain. All patients undergoing early ERCP for severe gallstone pancreatitis require endoscopic sphincterotomy whether or not stones are found in the bile duct (recommendation grades B and C).
	Patients with signs of cholangitis require endoscopic sphincterotomy or duct drainage by stenting to ensure relief of biliary obstruction (recommendation grade A).
	! All patients with biliary pancreatitis should undergo definitive management of gallstones during the same hospital admission, unless a clear plan has been made for definitive treatment within the next two weeks (recommendation grade C).
5. Management of necrosis	! All patients with severe acute pancreatitis should be managed in a high dependency unit or intensive therapy unit with full monitoring and systems support (recommendation grade B).
	! All patients with persistent symptoms and greater than 30% pancreatic necrosis, and those with smaller areas of necrosis and clinical suspicion of sepsis, should undergo image guided fine needle aspiration to obtain material for culture 7–14 days after the onset of pancreatitis (recommendation grade B).
	Patients with infected necrosis will require intervention to completely debride all cavities containing necrotic material (recommendation grade B).
	! The choice of surgical technique for necrosectomy, and subsequent postoperative management, depends on individual features and locally available expertise (recommendation grade B).
6. Provision of services	! Every hospital that receives acute admissions should have a single nominated clinical team to manage all patients with acute pancreatitis (recommendation grade C).
	! Management in, or referral to, a specialist unit is necessary for patients with extensive necrotising pancreatitis or with other complications who may require intensive therapy unit care, or interventional radiological,

	endoscopic, or surgical procedures (recommendation grade B).
--	--

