## Table\_3. Statements and Recommendations from the 2018 American Gastroenterological

Association Institute Guideline on Initial Management of Acute Pancreatitis.

1.	!	Recommendation 1A. In patients with AP, the AGA suggests using goal-directed therapy for fluid management. Conditional recommendation, very low quality evidence. Comment: The AGA makes no recommendation whether normal saline or Ringer's lactate is used.
	!	Recommendation 1B. In patients with AP, the AGA suggests against the use of hydroxyethyl starch (HES) fluids. Conditional recommendation, very low quality evidence.
2.	!	Recommendation 2. In patients with predicted severe AP and necrotizing pancreatitis, the AGA suggests against the use of prophylactic antibiotics. Conditional recommendation, low quality evidence.
3.	!	Recommendation 3. In patients with acute biliary pancreatitis and no cholangitis, the AGA suggests against the routine use of urgent ERCP. Conditional recommendation, low quality evidence.
4.	!	Recommendation 4. In patients with AP, the AGA recommends early (within 24 hours) oral feeding as tolerated rather than keeping the patient nil per os. Strong recommendation; moderate quality evidence.
5.	!	Recommendation 5. In patients with AP and inability to feed orally, the AGA recommends enteral rather than parenteral nutrition. Strong recommendation, moderate quality evidence.
6.	!	Recommendation 6. In patients with predicted severe or necrotizing pancreatitis requiring enteral tube feeding, the AGA suggests either nasogastric or nasoenteral route. Conditional recommendation, low quality evidence.
7.	!	Recommendation 7. In patients with acute biliary pancreatitis, the AGA recommends cholecystectomy during the initial admission rather than after discharge. Strong recommendation, moderate quality evidence.

From: Crockett SD, Wani S, Gardner TB, Falck-Ytter Y, Barkun AN; American Gastroenterological Association Institute Clinical Guidelines Committee. American Gastroenterological Association Institute Guideline on Initial Management of Acute Pancreatitis. Gastroenterology. 2018 Mar;154(4):1096-1101. doi: 10.1053/j.gastro.2018.01.032. Epub 2018 Feb 3. PMID: 29409760.

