13. Management of biliary pancreatitis	
 
! Early ERCP/ES should be performed in gallstone-induced acute pancreatitis when complications of cholangitis or prolonged passage disorder of the biliary tract are suspected. (1A)
 
! To prevent the recurrence of gallstone-induced acute pancreatitis, cholecystectomy is recommended for cases where such surgery is possible. (1B)
 
! A cholecystectomy should be performed as soon as gallstone-induced acute pancreatitis has been resolved. (1B)
 

14. Management of abdominal compartment syndrome	
 
The sequential measurement of IAP is recommended for cases with excessive fluid infusion, high severity, renal and respiratory complications, and fluid accumulation in multiple areas as observed by CT, since the onset of ACS increases the mortality rate in such cases. (2C)
 
When there is persistent or recurrent IAPЯ12mmHg, conservative treatment (gastrointestinal decompression, intra-abdominal decompression, improvement of abdominal wall compliance, appropriate fluid infusion and circulation management) should be initiated. The goal should be to manage for IAPIO5mmHg. Surgical decompression should be considered only when internal treatment is not effective for patients with IAP>20mmHg and where the additional complication of organ failure is of concern. (2D)
 

15. Interventions for the local complications	! In principle, conservative treatment should first be performed for necrotizing pancreatitis. The best indication for intervention is applied to cases of infected pancreatic necrosis with suspected or confirmed infection

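### The early definitive treatment rate is labelled as guideline-concordant care, but its two-week window and its acceptance of ERCP alone do not match the newer guidelines that the protocol tabulates, and the CRF cannot derive it as defined

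*Combined protocol and SAP*

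**What the plan says.** Under Secondary outcomes, the combined protocol and SAP defines the early definitive treatment rate, 2019 vs. 2020, as "treatment in accordance with the current guidelines (cholecystectomy or ERCP with endoscopic sphincterotomy during the same hospital admission or within 2 weeks of discharge". Either procedure counts, and no severity limit is stated. The Secondary objectives set the standard for compliance as the most up-to-date international guidelines.

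The protocol reprints the guidelines it relies on:

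- **Table 1 (WSES 2019), item 22.** "Laparoscopic cholecystectomy during index admission is recommended in mild acute gallstone pancreatitis". If ERCP and sphincterotomy have been done, the recurrence risk is lower, "but same admission cholecystectomy is still advised since there is an increased risk for other biliary complications". With peripancreatic fluid collections, "cholecystectomy should be deferred until fluid collections resolve or stabilize and acute inflammation ceases".
- **Table 2 (UK 2005), item 4.** Definitive gallstone management in the same admission, "unless a clear plan has been made for definitive treatment within the next two weeks" (grade C). No procedure is named.
- **Table 3 (AGA 2018), recommendation 7.** In acute biliary pancreatitis, "the AGA recommends cholecystectomy during the initial admission rather than after discharge". No severity limit is given.
- **2015 Japanese table, item 13.** To prevent recurrence, "cholecystectomy is recommended for cases where such surgery is possible", to be done once the pancreatitis has resolved.

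In the CRF, the ERCP field (Section 9) offers three time bands up to 72 hours, or no. The cholecystectomy field (Section 12) offers 3, 7 or 14 days, or delayed, and states no reference date. No discharge date or length of stay is listed.

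**The concern.** The outcome carries a label that its scoring rule does not earn. A patient who has ERCP and goes home with the gallbladder in place is scored as treated according to current guidelines, although Table 1 advises otherwise. So is a patient operated on ten days after discharge, although Table 3 advises otherwise. A patient whose surgery is deferred because of a fluid collection, as Table 1 advises, and who has no ERCP is scored as not treated accordingly.

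This matters because the Aim of the study argues that guidelines were disregarded more during the pandemic, and the Background section on Covid-19 singles out early definitive treatment as the recommendation at risk. This outcome is the most direct test of that idea. An unchanged composite could be read as guideline care having held in 2020 when cholecystectomy had in fact given way to ERCP alone or to surgery after discharge.

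**Working it through.** **1. Rule against tables**

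| Element of the rule | Table 1 (2019) | Table 2 (2005) | Table 3 (2018) | Japanese (2015) |
|---|---|---|---|---|
| Up to two weeks after discharge | Conflicts in mild disease | Nearest source, but requires a clear plan | Conflicts | Not addressed |
| ERCP alone is enough | Conflicts | Procedure not named | No such alternative printed | No such alternative printed |
| No exception for collections | Conflicts (deferral advised) | No exception printed | No exception printed | Surgery after resolution |

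The window has one source, the oldest table. Acceptance of ERCP alone is compatible with that table only because it names no procedure. The deferral point rests on Table 1 alone.

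**2. Contribution of ERCP alone**

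The plan gives no expected rate for this outcome, so there is no stated figure to reproduce. The Background reports a Swedish cohort in which 80% had definitive treatment: 68% of these by cholecystectomy, 17% by ERCP and sphincterotomy, 15% by both.

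- With cholecystectomy: 0.80 × (0.68 + 0.15) = 0.664
- ERCP alone: 0.80 × 0.17 = 0.136
- Share of treated patients without cholecystectomy: 0.136 / 0.80 = 17%

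**3. What the composite can detect**

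Assumptions: the Swedish rates apply in 2019; cholecystectomy falls by f = 10 points in 2020 (range 5 to 15); a fraction s of those patients get ERCP alone instead; the test is a two-sided chi-squared test at 0.05. The 200 per year is borrowed from the Sample size section, where it is the minimum for mortality.

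- Cholecystectomy in 2020 = 0.664 − f
- Composite in 2020 = 0.80 − f(1 − s)
- Power ≈ Φ[(d − 1.96·SE₀)/SE₁], where d is the difference in rates, SE₀ = √(2p̄(1−p̄)/200), p̄ is the mean of the two rates, and SE₁ = √([p₁(1−p₁) + p₂(1−p₂)]/200)

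For f = 0.10:

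- Cholecystectomy, 0.664 vs 0.564: SE₀ = 0.0487, SE₁ = 0.0484, Φ(0.09) = 54%
- Composite, s = 0, 0.80 vs 0.70: SE₀ = 0.0433, SE₁ = 0.0430, Φ(0.35) = 64%
- Composite, s = 0.5, 0.80 vs 0.75: SE₀ = 0.0418, SE₁ = 0.0417, Φ(−0.76) = 22%
- Composite, s = 1, 0.80 vs 0.80: no difference, so only the 5% type I error rate

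| Fall in cholecystectomy | Cholecystectomy component | Composite, none substituted | Half | All |
|---|---|---|---|---|
| 5 points | 18% | 22% | 9% | 5% |
| 10 points | 54% | 64% | 22% | 5% |
| 15 points | 86% | 92% | 42% | 5% |

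**4. Can the CRF produce the outcome?**

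The definition counts ERCP until two weeks after discharge, but the ERCP field has no answer for a procedure after 72 hours. It counts surgery by reference to discharge, but the cholecystectomy bands have no stated origin and no discharge date is collected. A cholecystectomy recorded as within 14 days may be before or after discharge. Patients with ERCP alone in the first 72 hours can be separated from the two fields. A move from index-admission to post-discharge surgery cannot.

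**5. Dates**

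Table 1's source line reads "2019 WSES guidelines for the management of severe acute pancreatitis. World J Emerg Surg. 2019 Jun 13". From 1 January to 12 June 2019 is 163 of 365 days, so Table 1 was unpublished for 45% of the comparison year. Table 3 (March 2018) predates both years.

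**The case against.** The strongest reply is that the composite is legitimate. The Background presents Tables 1 to 4 together as the societies' guidelines, Table 2 supports a two-week plan without naming a procedure, the reference list includes an audit that uses early definitive treatment as a quality indicator, and the Swedish study counts ERCP as definitive treatment. This stands, and it is why the composite should stay. It does not rescue the label: the objective asks for the most up-to-date guidelines, and the rule follows the oldest one.

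A second reply is that the pandemic need not have pushed patients towards ERCP alone. The Covid-19 section names postponement of non-urgent endoscopy as its first mechanism, so ERCP may have fallen too. This also stands. With no substitution the composite detects a 10-point fall more often than its cholecystectomy component (64% against 54%). If ERCP alone also fell by 5 points, the composite would go from 80% to 65% and detect that in 92% of studies.

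A third reply is that Secondary outcomes also lists early definitive treatment strategies among the compliance items, and that the two procedures have separate CRF fields. This stands in part: that item again joins the two procedures with and/or, so no comparison of components is specified.

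Finally, the conflict is not uniform. Only Table 3 contradicts the window outright, Table 1 does so for mild disease, and the Japanese table excludes neither a two-week delay nor patients unfit for surgery.

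**Conclusion.** The point holds for the label and for the data capture. As printed, the rule scores as compliant some care that Tables 1 and 3 advise against, and can score as non-compliant a deferral that Table 1 advises. In the Swedish illustration, ERCP alone makes up 13.6 of the 80 points. The printed CRF cannot derive the definition.

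How far the composite hides a change between years depends on a substitution fraction that the documents do not give. For a 10-point fall, detection runs from about 5% (full) through 22% (half) to 64% (none), against 54% for cholecystectomy. These figures rest on the Swedish rates, an assumed fall and a borrowed sample size; they illustrate and do not predict.

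A reader might infer three stronger things that the documents do not support:

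- **That the composite will miss the pandemic effect.** This needs every lost cholecystectomy to become ERCP alone, whereas the plan expects endoscopy to be postponed as well.
- **That the composite has no guideline basis.** Table 2 provides one.
- **That the Canadian audit in the Background bounds the ERCP-alone share.** Its one-quarter figure applies only to patients in whom index surgery was not possible. ERCP use in other unoperated patients is not given.

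The effect of deferred patients on the comparison between years cannot be sized from the documents.

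**What to change.** 1. Keep the composite for comparison with published audits, but remove the claim that it represents treatment according to current guidelines. Name Table 2 as its source.
2. Report by year cholecystectomy (with or without ERCP) and ERCP alone, overall and by Revised Atlanta grade, which CRF Section 4 already collects.
3. Use index-admission cholecystectomy in patients with mild disease as the compliance measure. Tables 1 and 3 agree on it, and Table 3 predates both years.
4. Apply points that rest on Table 1 alone, such as deferral with collections, only to admissions after 13 June 2019.
5. While data entry is open (to 31/08/2021), add a yes/no field for cholecystectomy during the index admission and an answer option for ERCP after 72 hours.
6. If the CRF cannot be changed, report the existing 3, 7 and 14-day and 72-hour categories and state that index-admission compliance cannot be separated.

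The cost is one field and one answer option, with a query to centres on records already entered. The rest is a re-cut of collected fields. Subgroup rates will be less precise, and patients unfit for surgery will still count as untreated; the ASA score in CRF Section 4 allows a check on that.

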A recent study from Singapore aiming to review the clinical management of patients with AP in an HPB referral center in the light of assessing the compliance to the 2013 International Association of Pancreatology (IAP)/American Pancreatic Association (APA) and the 2015 Japanese guidelines found that only 50% of patients received Ringer lactate for initial fluid resuscitation, 38.7% received antibiotics as prophylaxis, 21.4% of patients with severe AP had early enteral nutrition, and only 21.4% patients with biliary AP had index admission cholecystectomy despite the recommendations [13]. In

another recent study by a Canadian group, only 25% of patients with gallstones AP underwent a cholecystectomy on the same admission. Furthermore, only one-quarter of patients in whom an index admission cholecystectomy was not possible underwent ERCP with sphincterotomy, and only one-third of patients with gallstones AP and an imaging-confirmed obstructed common bile duct had an ERCP and sphincterotomy [14]. Slow implementation of the recommendation on early cholecystectomy has also been reported in a Danish survey seeking compliance with the recommendations of the national reference program for the treatment of patients with gallstone disease [15], and a similar lack of compliance with guidelines was found in Italy, mainly regarding indications for endoscopic and surgical management [16].

Conversely, a recent study from Sweden has shown that the recurrence rate and associated costs can be reduced by improved compliance to current AP guidelines. The authors found that 80% of patients with biliary AP underwent definitive treatment during their first attack (68% cholecystectomy, 17% ERCP and sphincterotomy, 15% both interventions) [17].

Moreover, significant overall differences between the practice of HPB specialists and non-specialists in gallstone AP have been reported, especially regarding severity assessment, indication and timing of requesting CT scan, nutritional support, and in common bile duct assessment before cholecystectomy [18].

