#### Section 7 – Diagnostic Imaging

! Initial diagnostic imaging (Ultrasound scan on admission/CT scan on admission/CT scan <24h/CT scan 24-48h/CT scan >48h)

- ! MRCP (MRCP on admission/MRCP <24h/MRCP >24h/No)
- ! Endoscopic ultrasound scan (Yes <24 hours/Yes >24 hours/No)
- ! Re-evaluation with CT scan (None/<7 days/7-14 days/15-30 days/>30 days)

Section 8 – Physical examination on admission (Localized abdominal pain/Localized abdominal rigidity/Diffuse abdominal pain/Diffuse abdominal rigidity/No abdominal pain/No abdominal rigidity)

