## Section 9 – Concomitant findings on admission

- ! Choledocholithiasis (Yes/Yes with common bile duct obstruction/No)
- ! Cholangitis (Yes/No)
- ERCP with sphincterotomy (Yes-within 24 hours/Yes within 24-48 hours/Yes within 48-72 hours/No)

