## Section 10 – 30-day Morbidity

- ! Gastric outlet obstruction (Yes/No)
- ! Pseudocyst (Yes/No)
- ! Infected necrosis (Yes/No)
- ! Endoscopic drainage of pseudocyst/walled-off necrosis (Yes/No)
- ! CT-guided fine needle aspiration in case of infected pseudocyst/walled-off necrosis (Yes/No)
- ! Surgical necrosectomy (Yes-laparoscopic/Yes-open/No)
- ! Timing of surgical necrosectomy (< 2 weeks from the onset of symptoms/2-4 weeks)>4 weeks)
- ! Setting of surgical necrosectomy (Upfront/After failure of endoscopic necrosectomy/After failure of endoscopic and percutaneous necrosectomy)
- ! Cystogastrostomy (Yes-endoscopic/Yes-surgical/No)
- ! Abdominal compartment syndrome (Yes/No)
- ! Open abdomen (Yes/No)
- ! Timing of re-exploration (24-48 hours/48-72 hours/>72 hours)
- ! Bleeding (Yes/No)
- ! Bowel ischemia (Yes/No)

- ! Bowel fistula (Yes/No)
- ! Necrotizing cholecystitis (Yes/No)

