## Section 11 – Medical Therapy

- ! Antibiotic prophylaxis (Yes/No)
- ! Antifungal prophylaxis (Yes/No)
- ! Use of somatostatin analogs (Yes/No)
- ! Nutritional support on admission (Oral/Enteral via nasogastric feeding tube/Enteral via nasojejunal feeding tube/Total parental nutrition/Nihil per os)

Section 12 – Cholecystectomy (Yes-within 3 days/Yes-within 7 days/Yes-within 14 days/No-delayed cholecystectomy)

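### The early definitive treatment rate, as defined, cannot be derived from the listed CRF fields: ERCP has no Yes code after 72 hours, and neither procedure field states when its clock starts

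*Combined protocol and SAP*

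**What the plan says.** The first secondary outcome is the early definitive treatment rate in 2019 against 2020, where a patient qualifies through "cholecystectomy or ERCP with endoscopic sphincterotomy during the same hospital admission or within 2 weeks of discharge". Early definitive treatment appears again in the same section as one of the attitudes by which compliance is judged.

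Two CRF fields could feed this outcome:

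- CRF Section 9: "ERCP with sphincterotomy (Yes-within 24 hours/Yes within 24-48 hours/Yes within 48-72 hours/No".
- CRF Section 12 (Cholecystectomy): "Yes-within 3 days/Yes-within 7 days/Yes-within 14 days/No-delayed cholecystectomy".

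Other timed fields are built differently. Some have an open-ended late code, such as "Endoscopic ultrasound scan (Yes <24 hours/Yes >24 hours/No" in CRF Section 7 and "Timing of re-exploration (24-48 hours/48-72 hours/>72 hours" in CRF Section 10. One states its origin: "Timing of surgical necrosectomy (< 2 weeks from the onset of symptoms", also in CRF Section 10.

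For the timing of the admission itself, the CRF records only the calendar year.

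**The concern.** The outcome is defined by an anchor (the index stay and its discharge) that the CRF does not record, and one of its two procedures is coded over a much shorter span than the definition allows. An ERCP with sphincterotomy on day 5 of the index stay, or ten days after discharge, meets the definition but fits none of the Yes codes. Unless that patient also has a cholecystectomy coded Yes, the database may show a compliant patient as untreated.

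At stake are the level of a named secondary outcome and the matching compliance item. The study sets out to show where guidelines are under-implemented, so an undercount would lean towards its expected conclusion. Recruiting more patients would not remove it.

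**Working it through.** **1. Definition against codes.**

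| | Definition (Secondary outcomes) | Last Yes code in the CRF | Stated origin |
|---|---|---|---|
| ERCP with sphincterotomy | any time in the index stay, or up to 14 days after discharge | 48-72 hours | none |
| Cholecystectomy | same | 14 days | none |

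For ERCP the mismatch holds whether time runs from onset, admission or discharge; even from discharge, 72 hours falls short of 14 days. CRF Sections 7, 9 and 10 contain seven timed fields: first imaging, MRCP, EUS, repeat CT, ERCP, necrosectomy and re-exploration. The other six have an open-ended late code; ERCP does not. The cholecystectomy field in Section 12 also has no late Yes code and places delayed surgery under No.

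**2. Cholecystectomy depends on the origin.**

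- Days from discharge, with in-stay operations coded Yes: the field covers the window.
- Days from admission, with a stay of L days: the codes end on day 14 and the window ends on day L + 14, so L days are uncovered. For an assumed 5-day stay, that is 5 of the 14 post-discharge days. For an assumed 20-day stay, it is all 14 plus 20 - 14 = 6 in-stay days.
- Days from onset: the codes end no later than they would from admission, so the gap is at least as large.

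The documents do not say how many operations fall in these days.

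**3. Repair at analysis.** CRF Sections 1 to 14 list no discharge date, length of stay, procedure date or interval, or index-admission flag. The window cannot be rebuilt.

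**4. Direction.** If the origin is onset, admission or discharge, a procedure truly within 72 hours or 14 days of it took place in hospital or no more than 14 days after discharge, so a correctly recorded Yes qualifies. If late ERCPs are coded No, the recorded rate is therefore at or below the true one. If they are left blank or given the nearest Yes, this no longer follows.

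**5. Illustrative size (ERCP only).** The documents give no figure for ERCP after 72 hours. The Background cites a Swedish study in which "80% of patients with biliary AP underwent definitive treatment during their first attack (68% cholecystectomy, 17% ERCP and sphincterotomy, 15% both interventions". Since 68 + 17 + 15 = 100, these are read as shares of treated patients.

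- ERCP-only share of all patients: e = 0.80 × 0.17 = 0.136, or 0.136 × 200 = 27 per 200 patients.
- Let f be the share of these treated after 72 hours and coded No (assumed). Loss = e × f; recorded rate = 0.80 - e × f.

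| f (assumed) | Loss (points) | Patients per 200 | Recorded rate if the true rate is 80% |
|---|---|---|---|
| 10% | 1.4 | 2.7 | 78.6% |
| 25% | 3.4 | 6.8 | 76.6% |
| 50% | 6.8 | 13.6 | 73.2% |
| 100% | 13.6 | 27.2 | 66.4% |

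**6. Year comparison, same mix.** Spurious difference = e × (f in 2020 - f in 2019), or 1.36 points for each 10-point difference in late share. Take 200 per group (Sample size section) and assume f = 25% in 2019. With f = 58% in 2020, the recorded rates are 76.6% and 72.1%.

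- SE = √(0.766 × 0.234/200 + 0.721 × 0.279/200) = 4.4 points.
- Bias = 0.136 × 0.33 = 4.5 points.

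The late share would thus have to differ by about 33 points before the bias reached one standard error.

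**The case against.** The strongest reply is that the ERCP field was never meant for this outcome. It stands beside choledocholithiasis and cholangitis, and the Secondary outcomes section has a separate compliance item on early ERCP in those conditions. The UK guideline reproduced in Table 2 also uses 72 hours, counted from onset of pain. The cut-off is therefore plausibly deliberate. That explains the field, but it leaves no other field to record a later ERCP for the definitive treatment rate.

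A second reply is that entry is through an online form whose field instructions are not in the documents, so sites may have been told the time origin. That is possible, and the heading of CRF Section 9 hints at admission for ERCP. Instructions on origin would settle the cholecystectomy question but would not add the missing ERCP code.

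Three stronger readings are tempting, and the documents do not support them:

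- *The recorded rate is certainly a lower bound.* This needs sites to code late ERCP as No, and an origin no later than discharge. Neither is stated.
- *The loss can be capped from the Canadian study.* A reader might apply its one-quarter ERCP rate to all patients without index cholecystectomy. The rate is given only for those in whom surgery was ruled out: "only one-quarter of patients in whom an index admission cholecystectomy was not possible underwent ERCP with sphincterotomy". Nothing is given for patients who could have had surgery but did not, so the product is not a maximum.
- *The 2019-2020 contrast is biased.* The COVID-19 section describes advice to put off endoscopy that was not urgent. Bias would need procedures to move past the coded limit yet stay inside the window, or the late share to differ between years for some other reason. Procedures pushed beyond the window are a true fall, correctly counted. Step 6 suggests that only a large shift would matter at the planned minimum size.

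**Conclusion.** The point stands in this form: the early definitive treatment rate, as defined, cannot be derived from the listed CRF fields. The ERCP gap follows directly from the response list. The cholecystectomy gap is conditional: it is absent if days run from discharge and present if they run from admission or onset.

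Undercounting is the likely direction, not a certain one, and its size is unknown. The 1.4-6.8 points are an illustration. They rest on the Swedish mix, which refers to treatment during the first attack and not to this protocol's window, and on an assumed late share of 10-50%. They exclude any loss of late cholecystectomies. Patients with a cholecystectomy coded Yes are unaffected by the ERCP gap.

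The main consequence is for the level of the rate and the compliance item. Distortion of the year comparison is possible but not shown. The 30-day mortality and morbidity outcomes have their own fields and are not affected. This should be fixed because the outcome is named and the remedy is cheap.

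**What to change.** Before data entry opens (01/03/2021 in Study periods):

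- Keep the existing timing bands, which serve the early-ERCP and timing items, and state the time origin for each.
- For ERCP with sphincterotomy and for cholecystectomy, add one field with the codes: index admission / within 14 days after discharge / later / not performed / unknown. Alternatively, record length of stay and days from admission to each procedure, as intervals and not dates, which fits the rule against identifiable data.
- Compute the outcome from these fields.

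The cost is two response lists or three interval fields per patient and slightly more abstraction. Procedures done at another hospital after discharge may need tracing, and some will end up as unknown.

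If the CRF cannot be changed, redefine the outcome to match the existing codes, state their origin, and report that it is narrower than the window now in the Secondary outcomes section. That costs only text, but the study then no longer measures the rate it set out to measure.
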